6.11.2.1 Sensitivity Analyses of the Primary Efficacy Endpoint

To assess the robustness of the findings from the primary analysis, the following sensitivity analyses will be conducted:

- Primary analysis will be repeated using the FAS population.
- Primary analysis will be repeated using the PP population with the actual treatment received.
- Primary analysis will be repeated with imputation of data which may have been affected by the intercurrent events. All per-visit Hb values within four weeks of administration of rescue therapy (narrow or broad-on-treatment defined in [Section 6.11.4.4](#)) or after EOT visit will be set as missing prior to imputation.
- Primary analysis will be repeated with method of mixed model for repeated measures (MMRM) based on observed data only. The MMRM model as described in [Appendix A](#) will include baseline Hb, stratification factor (dialysis organization), treatment group, analysis period (throughout 26-weeks), treatment-by-analysis time period interaction, baseline-by-analysis time period interaction as covariate.
- Tipping point analyses will be performed to assess the effect of the missing data.

-
- Primary analysis will be repeated for the vadadustat 900 mg TIW starting dose group vs. Mircera and the vadadustat 600 mg starting dose group vs. Mircera as exploratory analyses.

6.11.3 Secondary Efficacy Analyses

The study has one secondary efficacy endpoint which will be analyzed formally only if the primary analysis meets the noninferiority margin.

Mean change in Hb between Baseline (average pretreatment Hb) and the secondary evaluation period (average Hb from Weeks 46 to 52, inclusive) will be analyzed using the same methodology as specified for the primary efficacy endpoint. Evaluation of the average change in Hb will employ the approach described for the primary endpoint assessing Weeks 46 to 52 instead of Weeks 20 to 26.

Sensitivity analyses analogous to those performed for the primary efficacy endpoint will be repeated to assess mean change in Hb from Baseline to Weeks 46 to 52. For ANCOVA models, the analysis period of Weeks 46 to 52 will replace the analysis period of Weeks 20 to 26, and for MMRM, the models will be extended to include analysis period up to week 52. The analysis will be repeated for the vadadustat 900 mg TIW starting dose group vs. Mircera and vadadustat 600 mg starting dose group vs. Mircera as exploratory analyses.

After the non-inferiority for both primary and key secondary endpoints have been established, If the lower limit of the 2-sided 95% confidence interval for the difference between the mean Hb change from baseline to Weeks 20 to 26 in the vadadustat group and the mean Hb change from baseline in the Mircera group is above zero, superiority will have been established and the finding will be interpreted as providing evidence of a greater change from baseline in Hb for vadadustat relative to the control arm. Because the same 95% confidence interval is used to the superiority test, no adjustment for multiplicity is needed.

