3.3 SAMPLE SIZE DETERMINATION

For the primary efficacy analysis, it is assumed that the difference in mean change from Baseline in Hb for vadadustat will be the same as the active control, Mircera, and the common standard deviation for the mean change from Baseline will be assumed to be 1.2 g/dL. The noninferiority margin of -0.75 g/dL will be used (for vadadustat minus Mircera). With the 1:1:1 randomization ratio of vadadustat 600 mg TIW, vadadustat 900 mg TIW, and Mircera, and approximately 150 subjects in each arm, the noninferiority test will have >90% power with consideration of a 30% drop out rate.

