6.11.2 Primary Efficacy Analyses

The primary efficacy endpoint is defined as the mean change in Hb between Baseline (average pretreatment Hb) and the primary evaluation period (average Hb from Weeks 20 to 26, inclusive).

The primary analysis of the primary endpoint will use the randomized population with imputation of data. All intercurrent events will be handled by treatment policy strategy ([Section 6.11.1](#)). Unobserved data after intercurrent events, including Hb outcomes and any covariates to be used in the models, will be imputed with the randomized treatment group to which the subject was randomized using multiple imputation under fully conditional specification (FSC) method as described in [Appendix B](#). Data up to

scheduled visit of week 26 will be included in the primary efficacy analyses. Analysis of covariance (ANCOVA) as described in [Appendix A](#) will be used to calculate the LS mean (SE) by treatment group and LS mean difference (SE), 95% confidence intervals (CI) of the difference in mean change in Hb from baseline to the primary evaluation period between the vadadustat groups and Mircera control group, with the randomization stratification factor (Dialysis organization) and Baseline Hb as covariates.

Treatment comparisons will be performed between the vadadustat and Mircera groups. Subjects in the vadadustat starting dose groups of 600 mg or 900 mg TIW will have their doses adjusted to maintain Hb levels of 10.0 to 11.0 g/dL following the protocol's dosing algorithm.

- Noninferiority of vadadustat will be established if the lower limit of 2-sided CI is greater or equal to -0.75 g/dL for combined vadadustat dosing groups minus Mircera.

If the lower limit of the 2-sided 95% confidence interval for the difference between the mean Hb change from baseline to Weeks 20 to 26 in the vadadustat group and the mean Hb change from baseline in the Mircera group is above zero, superiority will have been established and the finding will be interpreted as providing evidence of a greater change from baseline in Hb for vadadustat relative to the control arm. Because the same 95% confidence interval is used to the superiority test, no adjust of multiplicity is needed.

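### The superiority rule in SAP 6.11.3 names Weeks 20-26, probably a carry-over slip; with the period corrected, the SAP still sets no order between primary superiority and the secondary tests

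*SAP*

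**What the plan says.** SAP 6.11.2 tests noninferiority at Weeks 20-26 (combined vadadustat minus Mircera, margin -0.75 g/dL). It then declares superiority at Weeks 20-26 if the lower limit of the two-sided 95% confidence interval is above zero. It sets no condition on the secondary endpoint, and it adds: "Because the same 95% confidence interval is used to the superiority test, no adjust of multiplicity is needed".

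SAP 6.11.3 deals with Weeks 46-52. The secondary endpoint is "analyzed formally only if the primary analysis meets the noninferiority margin", and its evaluation is to "employ the approach described for the primary endpoint assessing Weeks 46 to 52 instead of Weeks 20 to 26". The closing paragraph gives a superiority rule with a precondition, "After the non-inferiority for both primary and key secondary endpoints have been established, If the lower limit of the 2-sided 95% confidence interval", but the contrast that it then tests is the "difference between the mean Hb change from baseline to Weeks 20 to 26 in the vadadustat group" against Mircera. It ends: "Because the same 95% confidence interval is used to the superiority test, no adjustment for multiplicity is needed".

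Protocol 10.5.2 and 10.5.3 contain no superiority test. SAP section 7 and the SAP version table record the removal of a hierarchy between the two starting-dose comparisons; that hierarchy did not order the endpoints. SAP section 1 gives the SAP precedence over the protocol, which cannot settle a question inside the SAP.

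**The concern.** There are two problems.

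- **The period.** Read literally, 6.11.3 makes Weeks 20-26 superiority depend on noninferiority at both endpoints, while 6.11.2 makes the same claim with no secondary condition. The explicit rule for Weeks 46-52 superiority is then missing; that test enters only by reference to the primary methodology.
- **The order.** Replacing the period does not finish the job. Once primary noninferiority is met, primary superiority (6.11.2) and secondary noninferiority (6.11.3) are both open at one-sided 2.5%, and neither waits for the other. Secondary superiority follows noninferiority on both endpoints, but has no place relative to primary superiority.

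Using one interval for noninferiority and then superiority needs no adjustment because the two tests are nested on a single parameter. That reasoning does not reach across two parameters measured in two periods. At stake is whether the superiority conclusions, which the SAP treats as formal, carry the error rate implied, and whether the order could be chosen after the data are seen.

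**Working it through.** **Inputs.** From SAP 3.3: SD 1.2 g/dL, margin -0.75 g/dL, about 150 per arm, 30% dropout, and a true difference of zero ("it is assumed that the difference in mean change from Baseline in Hb for vadadustat will be the same as the active control, Mircera"). From SAP 6.11.2: combined vadadustat versus Mircera, two-sided 95% interval, so z = 1.96 per test. Completers: 0.7 × 300 = 210 and 0.7 × 150 = 105.

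**Assumptions.** The standard error is the same in both periods. The correlation ρ between the two period estimates is not in the documents, so a range is shown.

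**Step 1, the plan's own figure.**
- One arm versus Mircera: SE = 1.2 × √(1/105 + 1/105) = 0.1656; power = Φ(0.75/0.1656 − 1.96) = Φ(2.57) = 99.5%.
- Combined arms: SE = 1.2 × √(1/210 + 1/105) = 0.1434; power = Φ(0.75/0.1434 − 1.96) = Φ(3.27) = 99.95%.

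Both agree with the stated power above 90%, and neither is touched by this point.

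**Step 2, error with no order.** Write true differences as (Weeks 20-26, Weeks 46-52).
- At (0, -0.75), the claims that would be false are primary superiority and secondary noninferiority.
- At (0, 0), they are superiority in each period, if both are tested.

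In both cases the chance of at least one false claim is essentially 0.025 + 0.025 − P(Z₁ > 1.96 and Z₂ > 1.96), because the noninferiority steps in front are almost always passed.

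| ρ | P(both) | P(at least one false claim) |
|---|---|---|
| 0 | 0.0006 | 0.0494 |
| 0.5 | 0.0046 | 0.0454 |
| 0.8 | 0.0110 | 0.0390 |
| 0.9 | 0.0148 | 0.0352 |

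With no dropout (300 versus 150, SE 0.120) these rates change by at most 0.0001.

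**Step 3, the literal 6.11.3 condition.** If Weeks 20-26 superiority must wait for noninferiority on both endpoints, the error at (0, -0.75) falls to 2.5%. At (0, 0) it is again 4.9% to 3.5% if Weeks 46-52 superiority is also tested with no stated place. Keeping the literal text therefore does not remove the need for an order.

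**Step 4, one fixed sequence.** With primary noninferiority, secondary noninferiority, primary superiority, secondary superiority, stopping at the first failure, the error is 2.5% at both points. At (-0.75, -0.75) every version gives 2.5%, because secondary noninferiority is already conditional on primary noninferiority.

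**Step 5, how often the two conditions disagree.** They differ only when primary superiority is met and secondary noninferiority is not.
- At (0, 0) with ρ = 0: 0.025 × Φ(1.96 − 5.229) = 0.025 × 0.00054 = 0.0013%; less at higher ρ.
- At (0, -0.75): 0.025 − P(both) = 2.4%, 2.0%, 1.4%, 1.0% for ρ = 0, 0.5, 0.8, 0.9.

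**The case against.** The strongest reply is that this is a copying slip. That is probably right: 6.11.3 itself says that the secondary period takes the place of the primary one, its superiority paragraph nearly repeats 6.11.2, and a condition of noninferiority on both endpoints suits a secondary superiority rule. A reader might infer that the SAP deliberately sets two contradictory conditions for the Weeks 20-26 claim. The documents do not support that over the slip, and on the slip reading the conflict disappears. A reader might also infer that 6.11.3 already fixes the order of the tests; that follows only if the named period was intended.

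A second reply is that the effect is small and confined to supplementary claims. That also stands in part. The protocol plans no superiority test, and both noninferiority claims are protected. The 4.9% figure needs zero correlation between averages taken on the same subjects, and (0, -0.75) is a least-favourable case, not an expected one. One can construct true effects, such as +0.4 and -0.5, under which the two conditions give superiority probabilities of 0.80 and 0.38 at correlation 0.5, but nothing in the documents suggests those values, so no weight is put on them.

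The family counted here is also a choice. SAP 6.11.4.1 declares superiority for target-range proportions in both periods, and those claims are left out.

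What survives is the missing order. Correcting the period does not supply one, and the two no-adjustment sentences remain wrong across endpoints.

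**Conclusion.** The point holds as a wording and ordering defect that should be fixed. The period named in the 6.11.3 superiority rule is most likely wrong. With it corrected, primary superiority and the secondary tests have no stated order, and the claim that no adjustment is needed is valid only for noninferiority followed by superiority on one endpoint.

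The excess is from a nominal one-sided 2.5% to between 4.9% and 3.5%, with 3.5% to 3.9% the more realistic part because the same subjects are measured in both periods. It arises at the planning assumption of no difference if superiority is tested in both periods. The figures rest on 210 versus 105 completers, SD 1.2, equal standard errors and an assumed correlation.

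It would be wrong to conclude that the noninferiority findings or the sample size are in doubt. It would also be wrong to say that the choice of condition would often change the Weeks 20-26 conclusion under the planning assumption, where the two disagree in 0.0013% of trials or fewer.

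**What to change.** Before database lock:

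1. In the 6.11.3 superiority rule, change the period to Weeks 46 to 52. If no secondary superiority claim is meant, delete the paragraph and say that the methodology carried over from the primary endpoint covers noninferiority only.
2. State one fixed sequence in both 6.11.2 and 6.11.3, each step at two-sided 5%, stopping at the first failure. An example is primary noninferiority, secondary noninferiority, primary superiority, secondary superiority. This is a suggestion that protects secondary noninferiority, not an order that the SAP already sets. Another single order also controls the error, but putting primary superiority ahead of secondary noninferiority would cut the chance of showing secondary noninferiority from 99.9% to 2.5% when both true differences are zero.
3. Limit both no-adjustment sentences to noninferiority followed by superiority within one endpoint.

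The cost is SAP wording: no change to data, sample size, power or, under the example order, either noninferiority test. The downside of the example order is that primary superiority can be claimed only after secondary noninferiority. The loss is negligible when both true differences are zero and grows only if the Weeks 46-52 effect lies near or beyond the margin.

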6.11.4 Other Efficacy Analyses

Except for specifying the analysis population, other efficacy endpoint analyses will be performed using the randomized analysis population.

6.11.4.1 Hb value within the target range

All subjects will be defined as either being in target range (10.0 to 11.0 g/dL) in Weeks 20 through 26 (“yes”) or not (“no”), based on at least one Hb value meeting the target range during the visit windows in Weeks 20 through 26. This analysis includes the observed Hb values only.

The same criterion will be used based on the average Hb value during the visit windows in Weeks 20 through 26. To ensure uniformity across all analyses, the missing binary outcomes will be computed from the imputed complete dataset in the primary analysis.

The proportion of subjects within target range will be calculated, 95% CI for the proportions will be reported along with the difference in proportions as well as the odds ratio; a Mantel-Haenszel method stratified by dialysis organization will be used to calculate the 95% CI for the statistics of treatment comparison.

Noninferiority will be evaluated using a 2-sided CI for the difference in proportions. Noninferiority will have been established if the lower limit of the CI is above -15%.

If the lower limit of the 2-sided CI for the difference in proportions is above zero, superiority will have been established and the finding will be interpreted as providing evidence of a higher proportion of subjects being within the target range for vadadustat relative to the control arm.

Secondary evaluation period (Weeks 46 through 52) will be analyzed using the same method.

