5.3 OTHER EFFICACY ENDPOINTS

Other endpoints include the following:

- Proportion of subjects having a Hb value within the target range (10.0 to 11.0 g/dL) during the primary evaluation period (Weeks 20 to 26).
- Proportion of subjects having a Hb value within the target range (10.0 to 11.0 g/dL) during the secondary evaluation period (Weeks 46 to 52).
- Proportion of subjects having average Hb value within the target range (10.0 to 11.0 g/dL) during the primary evaluation period (Weeks 20 to 26)
- Proportion of subjects having average Hb value within the target range (10.0 to 11.0 g/dL) during the secondary evaluation period (Weeks 46 to 52)
- Mean change from baseline and percentage change from baseline in the primary efficacy period (PEP) and secondary efficacy period (SEP) for iron-related parameters
- Proportion of subject receiving rescue by analysis periods.
- Proportion of subjects receiving RBC transfusions by analysis periods.
- Proportion of subjects receiving ESA medication by analysis periods.
- Time to first rescue by narrow and broad (include any rescue, ESA, and RBC respectively)
- Proportion of subjects who received any IV iron therapy by analysis period)
- Mean weekly IV dose elemental iron by analysis period and route of administration
- Mean change in serum glucose and lipid parameters between Baseline and the PEP (Weeks 20 to 26) and SEP (Weeks 46 to 52)
- Mean change in iron metabolism (including iron, hepcidin, ferritin, transferrin saturation [TSAT], total iron binding capacity [TIBC]) between Baseline and the PEP (Weeks 20 to 26) and SEP (Weeks 46 to 52)

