6.2 VISIT AND ANALYSIS TIME PERIOD CLASSIFICATION

All assessments will be mapped to the corresponding analysis visit (i.e., target week) based on study day, including unscheduled visits. [Table 1](#) is a general window for each visit based on the protocol. [Table 2](#) will be applied for less frequent assessments such as

[REDACTED] C-Reactive Protein (CRP), Complete Blood Count (CBC) with differential, Serum Chemistry, Lipid Panel, Reticulocyte count, Biomarkers, Erythropoietin and Dialysis Adequacy. All other assessments will apply to the analysis window from Table 1.

If more than one Hb assessment is available in a post-baseline analysis period (i.e., PEP or SEP), then all results will be used to calculate the average of Hb. But if more than one record is available in same day, the last assessment (i.e., at most one record per day) will

be used to calculate the average. For other assessments, if more than one assessment is available in each window, the assessment which is closest to the target day will be used for analysis. If the assessments are equally close, the last assessment will be used.

Table 1. Classification of Assessments at Every Visit (General)

Analysis Time Period	Visit	Target Day	Analysis Window
Baseline	Screening Visit 1	-	-
	Screening Visit 2	-	-
Week 2-6	Baseline	Day 1	<=Day 1 (prior to first dose) ^a
	Week 2	Day 14	Day 1 (post dose) – 21
	Week 4	Day 28	Day 22 – 35
Week 8-16	Week 6	Day 42	Day 36 – 49
	Week 8	Day 56	Day 50 – 70
	Week 12	Day 84	Day 71 – 98
Primary Efficacy Period (PEP) (Weeks 20-26)	Week 16	Day 112	Day 99 – 126
	Week 20	Day 140	Day 127 – 154
	Week 24	Day 168	Day 155 – 175
Week 30-42	Week 26	Day 182	Day 176 – 196
	Week 30	Day 210	Day 197 – 224
	Week 34	Day 238	Day 225 – 252
	Week 38	Day 266	Day 253 – 280
Secondary Efficacy Period (SEP) (Weeks 46-52)	Week 42	Day 294	Day 281 – 308
	Week 46	Day 322	Day 309 – 336
	Week 50	Day 350	Day 337 – 357
Safety Follow-up ^b	Week 52	Day 364	Day 358 – 378 or ET/EOT assessment date + 15 days
	Follow-up	ET/EOT assessment date + 28 days	>= ET/EOT assessment date + 15 days

^a If patient has no first dose date, day 1 will be the randomization date.

^b for Vital Sign, Dialysis Access Type, and Therapeutic Phlebotomy

Table 2. Classification of Assessments for Selected Assessment

Analysis Time Period	Visit	Target Day	Analysis Window
Baseline	Screening Visit 1	-	-
	Screening Visit 2	-	-
	Baseline	Day 1	<=Day 1 (prior to first dose) ^a
Week 2-6	Week 4	Day 28	Day 1 (post dose) – 49

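### The any-value version of the target-range endpoint should be descriptive: one in-range Hb in the period counts as success, yet noninferiority and superiority can be declared on it

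*SAP*

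**What the plan says.** SAP 6.11.4.1 defines two versions of the endpoint for Weeks 20 to 26.

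- **Any-value version.** A subject is a yes "based on at least one Hb value meeting the target range during the visit windows in Weeks 20 through 26". On data, it adds: "This analysis includes the observed Hb values only".
- **Average version.** "The same criterion will be used based on the average Hb value during the visit windows in Weeks 20 through 26". Here "the missing binary outcomes will be computed from the imputed complete dataset in the primary analysis". SAP 5.3 lists it as an endpoint in its own right: "Proportion of subjects having average Hb value within the target range".

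The decision rules follow both definitions and name neither. For noninferiority: "Noninferiority will have been established if the lower limit of the CI is above -15" per cent. Then: "If the lower limit of the 2-sided CI for the difference in proportions is above zero, superiority will have been established". The section ends by applying the same method to Weeks 46 to 52.

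Four other places bear on the point.

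- SAP 6.2 states "All assessments will be mapped to the corresponding analysis visit (i.e., target week) based on study day, including unscheduled visits". For Hb its only stated limit is one record per day.
- SAP 6.11.3 sets a testing order for the two Hb-change endpoints only.
- Protocol 4.4 lists the target-range proportions as other endpoints, with no margin. SAP section 7 does not list the added claims among the changes.
- Protocol 7.1.2 sets the treatment aim as reaching and keeping Hb in range with few excursions.

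**The concern.** The treatment aim is maintenance. One in-range value in a 70-day window does not show maintenance: a subject with 8.8, 9.0 and 10.1 g/dL is a yes, although the average is 27.9/3 = 9.3. A rule that is easy to meet pushes both arms towards high rates and shrinks differences between them, which matters most when the claim is noninferiority.

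Two versions, two periods and two claims give 2 × 2 × 2 = 8 possible statements that something has been established, none of them in the testing order. A report could quote whichever succeeded.

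The denominator is also unclear. SAP 6.11.4 uses the randomized population and 6.11.4.1 speaks of all subjects, but the any-value version uses only observed values. Under Protocol 8.1.2, subjects who permanently stop study medication leave the study, so many may have no value in the period.

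**Working it through.** **The plan's own figure.** The only stated power is for the primary endpoint: above 90% with 150 per arm, 30% dropout, SD 1.2 and margin 0.75 g/dL. With 150 × 0.7 = 105 per arm, SE = 1.2 × √(2/105) = 0.166, and power = Φ(0.75/0.166 − 1.96) = 99.5%. That statement holds. No expected rate or power is given for the target-range endpoint.

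**Inputs.** The primary period runs from Day 127 to Day 196 (SAP Table 1), which is 196 − 127 + 1 = 70 days, with scheduled Hb at Weeks 20, 24 and 26, so k = 3. The documents give no Hb mean or variance components for this period. I assumed a population mean of 10.3 to 10.5, between-subject SD of 0.5 to 0.7 and within-subject SD of 0.4 to 1.0 g/dL.

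**Model.** Hb = subject mean + independent normal noise, rounded to 0.1 g/dL. Any-of-k is yes if at least one of k values lies in 10.0 to 11.0; the average rule uses the mean of three. The extremes of the grid, in per cent:

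| Mean / between SD | Within SD | Single value | Any of 3 | Any of 4 | Average of 3 |
|---|---|---|---|---|---|
| 10.3 / 0.7 | 0.4 | 49.2 | 73.8 | 78.1 | 50.1 |
| 10.3 / 0.7 | 0.9 | 36.5 | 72.4 | 81.0 | 43.5 |
| 10.3 / 0.7 | 1.0 | 34.3 | 70.2 | 79.4 | 42.2 |
| 10.5 / 0.5 | 0.4 | 61.1 | 87.2 | 90.8 | 65.3 |
| 10.5 / 0.5 | 0.9 | 40.6 | 78.4 | 86.7 | 52.6 |

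**Level.** Any-of-3 runs from about 70 to 87%, the average from 42 to 65%.

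**Sensitivity to lost stability (within SD 0.4 to 0.9).** Single values fall by 49.2 − 36.5 = 12.7 to 61.1 − 40.6 = 20.5 points. The average version falls by about 6 to 13. Any-of-3 falls by 73.8 − 72.4 = 1.4 to 87.2 − 78.4 = 8.8.

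**Effect on the decision.** Suppose the vadadustat arms combined have within SD 0.9 and Mircera 0.4, in the first setting (10.3 / 0.7).

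- Any-value, 210 against 105 observed: half-width = 1.96 × √(0.738×0.262/105 + 0.724×0.276/210) = 10.4 points. Expected lower limit −1.4 − 10.4 = −11.8, which passes −15.
- Average, even with all 300 against 150: half-width = 1.96 × √(0.501×0.499/150 + 0.435×0.565/300) = 9.8. Expected lower limit −6.6 − 9.8 = −16.4, which fails.

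In the other setting (10.5 / 0.5) the any-value lower limit is −8.8 − 8.5 = −17.3 and also fails. Masking is possible, not certain.

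**Extra values.** A fourth value adds 3.6 to 9.2 points (about 4 to 9) to the any-value rate, and at most about 3 to the average. That the any-value rate cannot fall when a value is added follows from its definition; only the size rests on the assumptions.

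**Subjects with no value.** As an illustration, take 80% in range among observed subjects in both arms. Borrow 60.5% and 88.9% as the shares observed, from treatment completion in the earlier epoetin-conversion study in Protocol 3.4. Excluding the rest gives 80 − 80 = 0. Counting them as no gives 0.8 × 60.5 − 0.8 × 88.9 = 48.4 − 71.1 = −22.7 points, beyond the margin.

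**The case against.** - **The better version is already planned.** The any-value rule follows the protocol's endpoint wording, and the SAP adds the average version with imputation. This stands, and it makes the fix cheap. It does not limit the claims to that version.
- **These are other endpoints.** No primary or secondary conclusion depends on them. This stands and limits the weight of the point, but the SAP still uses the language of established noninferiority.
- **The missing-data rule may sit in blacked-out text.** SAP 6.3 refers to Appendix B, much of which is not visible, and classing all subjects could be read as no value = no. So the point is limited to the visible text. SAP Table 3 does state its rule for the Hb safety endpoints, so a matching line here is easy to add.
- **A reader might infer that the rule rewards unstable Hb.** Not in general. For a subject centred at 10.5, any-of-3 falls from 99.5% to 80.4% as within-subject SD goes from 0.4 to 1.0. It rises (34% to 60%) for a subject whose true mean is 9.5 or 11.5. In the populations tabulated it falls slightly between SD 0.4 and 0.9. Masking is the accurate word.
- **A reader might infer that extra testing favours vadadustat.** The documents do not show this. SAP 3.5 plans identical visits and assessments in all groups, and SAP 6.1 uses central-laboratory Hb. SAP 3.1 says that central Hb guides both drugs, although it also says that Mircera follows standard-of-care measures. Bias needs unscheduled central tests that differ by arm. The full 4 to 9 points would need every subject in one arm, and none in the other, to have a fourth value. An excess of 20% of subjects would give 0.2 × 4 to 0.2 × 9, about 1 to 2 points. That every unscheduled value counts under the any-value rule is itself a reading of SAP 6.2, whose all-results rule is written for the average.
- **The average does not measure stability well either.** Values of 8.5, 10.1 and 12.5 average 10.4 and pass both rules. This stands; the average is the better of the two, not a complete measure.

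**Conclusion.** The point holds as an inexpensive improvement to an other endpoint. As written, noninferiority or superiority can be declared on a rule that one in-range value satisfies, that rises with each added value, and that loses only about 1 to 9 points where single values in range lose 13 to 20. The sizes rest on assumed means and SDs. The documents establish the wording, the unrestricted claims and their place outside the testing order. They do not establish a bias between arms. The 22.7-point swing from the treatment of subjects without a value is an illustration with borrowed completion rates, not a forecast, but it shows that the result can turn on a rule the visible text does not give.

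**What to change.** Amend SAP 6.11.4.1 before database lock:

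1. Apply the noninferiority and superiority statements only to the average-Hb version with the primary multiple imputation, in each period, and label them nominal because they lie outside the SAP 6.11.3 order.
2. Report the any-value version descriptively, with one value per scheduled visit. The closest-to-target-day rule in SAP 6.2 could serve.
3. State whether a subject with no observed Hb in the period is a no or is excluded, and give the number of such subjects by arm.

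An optional addition is each subject's share of scheduled values in range, reported descriptively, since it speaks more directly to maintenance.

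The cost is SAP wording and small changes to table shells; both data sets are already planned. The downside is that one fewer endpoint carries a claim.
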